11.7.4. Physical examination

Physical examination data will be presented in data listing. In addition, proportion of subjects with at least one new abnormal physical examination findings will be summarized by cohort and treatment group and protocol specified collection time point, using frequency tabulations.

11.7.5. Others

The following other safety measures will be listed only:

- Subject Questionnaire
- Domiciled Status
- General Comment

12. HEALTH OUTCOMES ANALYSES

Not applicable for this study.

13. CLINICAL PHARMACOLOGY DATA ANALYSES

13.1. Pharmacokinetic Analyses

As L-dopa is produced endogenously, pre-dose plasma concentrations, as well as post-dose concentrations for placebo subjects, may be observed. To account for circulating endogenous L-dopa, PK parameters will be estimated from both actual measured (i.e. uncorrected) concentration data and individual baseline (pre-dose) corrected data. For placebo subjects with measurable L-dopa concentrations, PK parameters will only be estimated using uncorrected concentration data.

Carbidopa plasma concentration-time profiles (Cohort 4 only) will be evaluated to address the exploratory objective of this study where data permit. PK parameters will be determined for carbidopa using non-compartment analysis (NCA) techniques, at the discretion of the PK scientist.

Baseline corrected concentrations will be calculated by subtracting the pre-dose concentration value from the measured value for each post-dose sample. Pre-dose concentrations reported as “BLQ” will be set to a value of zero for adjustment of post-dose concentrations (i.e. post-dose concentrations will not change if pre-dose concentration is “BLQ”). Post-dose concentrations reported as “BLQ” will remain as “BLQ” (i.e. no correction applied). Post-dose concentrations that are negative after correction will be set to the value “BLQ”. Concentrations that are lower than the assay lower limit of quantification after correction (but positive in value) will be retained and the corrected value will be used in the PK parameter estimation (i.e. maximize the data that is available for PK parameter estimation).

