Subjects may be domiciled at the clinic overnight to enable scheduled assessments on the morning of, and prior to, Visit 2 (standard medications) and Visit 3 (test article) dosing, or will have transport provided to ensure they arrive at the clinical research unit on the morning of Visit 2 and Visit 3. Regardless of time of arrival at the study site, all subjects will be required to suspend dosing of usual PD medication (e.g. regular Madopar® or Sinemet® doses, DAS and/or COMT inhibitors doses and any required anti-OFF medication [e.g. Madopar rapid]) from 22:00 pm on Day-1, the day prior to study dosing. Suspension of usual PD medication will include on the morning of Day-0.

On Day-0, upon arrival at the research site (or upon waking if the subject was domiciled overnight at the research unit), and at 60 ± 5 minutes before dosing with INP103 or placebo, all subjects in Cohorts 1, 2, and 3 will take oral benserazide hydrochloride (benserazide) 25 mg (provided by the Sponsor). Subjects in Cohort 4 will NOT receive oral benserazide. Subjects who arrive at the study site on Day-0 (or who were domiciled overnight) and are determined by the Investigator to be in an ON state up to the scheduled time of dosing will not be dosed and will be excluded from further study participation but may be replaced at Sponsor's discretion.

On their scheduled day of dosing (Day-0; or on arrival at the unit on Day-1), eight subjects in each of three dose cohorts (35, 70 or 140 mg of INP103 L-dopa) and at least eight (8) (maximum 12) subjects in Cohort 4 (70/7.0 mg of INP103 L-dopa:carbidopa) will be randomized in a 3:1 fashion to one of two treatment arms. All subjects in Cohorts 1, 2 and 3 will receive oral benserazide 25 mg 60 ± 5 minutes before dosing with the study drug. Subjects in Cohort 4 will not receive oral benserazide before dosing with the study drug:

- INP103 (n=6 or maximum 9 in Cohort 4)

CONFIDENTIAL AND PROPRIETARY

- Placebo (n=2 or maximum 3 in Cohort 4)

Use of usual anti-PD medication (usual regular dosing [e.g. regular Madopar or Sinemet] and use of anti-OFF treatment, if required) may resume at 120 minutes after use of INP103 or placebo.

Subjects will be monitored for 7 days after the final administration of INP103 or placebo. All subjects will be observed as in-patients for at least 240 minutes post-dosing at visit 3. Follow-up evaluations will occur 7 days after dosing.

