13.1.1. Concentration-Time Data

Individual uncorrected and baseline corrected plasma L-dopa concentration-time data will be listed for each subject with actual sampling time (for placebo subjects only uncorrected concentrations will be listed). Plasma uncorrected and baseline corrected concentration-time data will be summarized by treatment and nominal sampling time point with descriptive statistics (number of non-missing observations, arithmetic mean, SD, median, minimum, maximum, geometric mean and coefficient of variation [CV%]). The number of values below limit of quantification (BLQ) will also be presented.

Concentrations that are BLQ will be treated as zero for the computation of descriptive statistics, except geometric mean. For the calculation of the geometric mean, concentrations that are BLQ will be treated as equal to the limit of quantification (LOQ). Missing values will be omitted from the calculation of descriptive statistics.

Individual and mean uncorrected and baseline corrected L-dopa concentration-time profiles for each dose regimen will be presented graphically on both linear and logarithmic concentration scales. Actual sampling times will be used for the graphical presentation of individual concentration-time data, and nominal sampling times will be used for mean concentration-time plots. For plots with a linear concentration scale, BLQ concentrations will be plotted as zero values. For plots with a logarithmic concentration scale, BLQ and zero mean values will not be plotted.

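### Negative baseline-corrected L-dopa values are relabelled BLQ and can then count as the LOQ, above small positive values that are kept, so a corrected geometric mean can exceed the arithmetic mean

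*SAP*

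**What the plan says.** SAP Section 13.1 corrects L-dopa for endogenous and residual levels by subtracting the pre-dose value from each post-dose value. Two rules follow.

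- Below zero: "Post-dose concentrations that are negative after correction will be set to the value" BLQ.
- Above zero but below the assay limit: "Concentrations that are lower than the assay lower limit of quantification after correction (but positive in value) will be retained". The stated use is that "the corrected value will be used in the PK parameter estimation".

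A post-dose sample that the assay reports as BLQ stays BLQ and is not corrected.

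Section 13.1.1 then sets the summaries: "Plasma uncorrected and baseline corrected concentration-time data will be summarized by treatment and nominal sampling time point with descriptive statistics". For BLQ values it says "Concentrations that are BLQ will be treated as zero for the computation of descriptive statistics, except geometric mean". The exception is "For the calculation of the geometric mean, concentrations that are BLQ will be treated as equal to the limit of quantification". The number of BLQ values is also to be shown. The corrected summary is Table 14.2.1.1.2.

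Section 13.1.2 gives three treatments of BLQ in the non-compartmental analysis, for uncorrected and corrected data alike. A BLQ value before the first quantifiable value becomes 0. One at the end of the profile after Cmax becomes missing. One between two quantifiable values becomes the LOQ, unless the PK scientist justifies excluding it. No separate rule covers values that are BLQ only because the subtraction made them negative.

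**The concern.** An assay-BLQ sample is never corrected, so any value that is negative after correction comes from a sample the assay did quantify, at a level below the subject's own pre-dose level. It is not below the limit of quantification in the assay sense, yet it takes that label and the BLQ conventions.

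Two results look wrong. First, a lower corrected value can be scored above a higher one. Secondly, the arithmetic and geometric means at one time point use different numbers (0 and the LOQ) for the same sample. For a single set of positive data the geometric mean cannot exceed the arithmetic mean, so a table showing this would look like a programming error. The BLQ count would also mix assay non-detects with subtraction artefacts.

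Negative values are plausible here. Section 13.1 expects measurable pre-dose L-dopa. Subjects may take up to 1200 mg/day of L-dopa, withheld only from 22:00 the evening before, so residual levels may still be falling. Cohort 4 is sampled from 4 minutes after dosing, when little drug may have been absorbed. How often this will happen cannot be read from the documents.

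**Working it through.** The plan states no figure on this point, so there is none to reproduce.

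**Inputs**
- Negative corrected value: BLQ. Positive corrected value below the LOQ: kept (SAP 13.1).
- BLQ: 0 in the arithmetic mean (AM), LOQ in the geometric mean (GM) (SAP 13.1.1).
- Active subjects per dose group: n = 6, up to 9 in Cohort 4 (SAP 4).
- LOQ: not given. Results are in multiples of the LOQ and scale with it, except step 1, which assumes LOQ = 10 for illustration.
- The concentrations below are invented to show how the rule behaves. They are not predictions.

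**Step 1: ranking.** Five subjects are at 20, 30, 40, 50 and 60. The sixth varies, and GM = exp(mean of ln x). For a sixth value of -1, GM = (20 × 30 × 40 × 50 × 60 × 10)^(1/6) = 29.94.

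| Sixth corrected value | Counted in GM as | GM |
|---|---|---|
| -1 | 10 | 29.94 |
| +1 | 1 | 20.40 |
| +5 | 5 | 26.67 |
| +9.9 | 9.9 | 29.89 |
| +10 | 10 | 29.94 |

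A negative value scores the same as one at the LOQ, and above every retained positive value below it.

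**Step 2: a mixed example in LOQ units.** Corrected values are -0.5, -0.2, 0.1, 0.3, 0.6 and 1.5.
- AM = (0 + 0 + 0.1 + 0.3 + 0.6 + 1.5)/6 = 2.5/6 = 0.42
- GM = (1 × 1 × 0.1 × 0.3 × 0.6 × 1.5)^(1/6) = 0.027^(1/6) = 0.55

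This assumes that retained sub-LOQ values enter the concentration summary. If they are treated there as BLQ instead, AM = 1.5/6 = 0.25 and GM = (1^5 × 1.5)^(1/6) = 1.07. The inversion in the table becomes a tie, but GM still exceeds AM.

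**Step 3: when GM exceeds AM.** Let k of n subjects be negative and the rest be at c × LOQ. Then, in LOQ units, GM = c^((n-k)/n) and AM = c(n-k)/n, so GM > AM when c < (n/(n-k))^(n/k).

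| n = 6, number negative | GM > AM if c is below |
|---|---|
| 1 | 2.99 |
| 2 | 3.38 |
| 3 | 4.00 |
| 4 | 5.20 |
| 5 | 8.59 |

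For n = 9 with 1 to 8 negatives, the thresholds run from 2.89 to 11.84. Two checks with one negative among six:
- Others at 2 × LOQ: AM = 10/6 = 1.67, GM = 2^(5/6) = 1.78. GM is higher.
- Others at 4 × LOQ: AM = 20/6 = 3.33, GM = 4^(5/6) = 3.17. GM is lower.

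**Step 4: non-compartmental analysis.** A negative value before the first quantifiable one is set to 0, so no LOQ is substituted. One between quantifiable values is set to the LOQ, while a small positive corrected value in the same place is kept. Here the inversion follows from explicit text, because retention is stated to be for parameter estimation. If the adjacent intervals have lengths h1 and h2, using the LOQ instead of 0 adds at most LOQ × (h1 + h2)/2 to AUC. That is the fully linear case; the plan's log-down rule gives less on the falling side. For the Cohort 4 sample at 44 minutes, between 29 and 59, the limit is LOQ × (15 + 15)/2 = 15 LOQ·min, or 0.25 LOQ·h.

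**The case against.** Much of the case against a serious reading stands.

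- **Early exposure.** A reader might infer that early AUC is biased upward. The documents do not support this. Section 13.1.2 sets BLQ values before the first quantifiable value to 0, which is where early negatives would usually fall.
- **Placebo.** A reader might also extend the point to placebo groups, where all-BLQ samples would give an arithmetic mean of 0 and a geometric mean at the LOQ. Sections 13.1 and 13.1.1 restrict placebo parameters and concentration listings to uncorrected data, so that example involves no negative corrected value. It is the ordinary BLQ convention and a separate matter.
- **Unstated reading.** The SAP names parameter estimation as the use of retained sub-LOQ values and is silent on the concentration table. The inversion in that table therefore depends on a reading. The geometric mean exceeding the arithmetic mean does not.
- **Low consequence.** Table 14.2.1.1.2 is descriptive and Priority 2. The PK/PD graph and the interim PK parameters use uncorrected data. The secondary PK endpoints and dose proportionality use Cmax, Tmax and AUC, not the table's geometric mean.
- **Embedded values.** The PK scientist may exclude an embedded BLQ value with justification.
- **Limits of the fix.** Setting negatives to 0 while keeping small positives is still one-sided truncation, so it does not remove all upward bias. Blanking the geometric mean is partly a matter of preference. A BLQ count is already planned, although as written it would not separate the two kinds of BLQ.

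None of this removes the defect: the rule as written can rank a lower value above a higher one and uses two different numbers for one sample in adjacent statistics.

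**Conclusion.** The point holds as a minor defect in the handling rules. It reaches the geometric means in the corrected-concentration summary and, through negatives lying between quantifiable values, the corrected AUC, including the AUC0-2h used for dose proportionality. No primary or motor endpoint is affected.

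Its size depends on how many corrected values are negative and how close the others lie to the LOQ. With six subjects and a common value for the positives, one negative is enough if the others are below about 3 × LOQ. At 4 × LOQ it no longer happens with one negative. The conclusion does not depend on the numerical LOQ. It does assume that some corrected values will be negative, which the documents make plausible but do not quantify.

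**What to change.** Amend SAP Sections 13.1 to 13.1.2 before database lock.

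1. Set negative corrected values to 0 in arithmetic summaries and wherever they occur in the corrected profile for the non-compartmental analysis. Use the linear trapezoid for any interval touching 0, because the log-down rule is undefined there.
2. Count them separately from assay BLQ.
3. State whether retained positive sub-LOQ values enter the concentration summaries.
4. Do not substitute the LOQ for a negative value in the geometric mean. Either compute it on positive values only, showing the number excluded, or leave it blank at time points with negative corrected values.

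The cost is wording, plus a few geometric means that are blank or rest on fewer subjects. With the mixed example above and positives only, GM = 0.027^(1/4) = 0.41 on four subjects, beside AM 0.42 on six. The positives-only option does not guarantee the usual ordering, because the two means then rest on different subjects: with one negative and five at 2 × LOQ it gives GM 2.00 (n = 5) beside AM 1.67 (n = 6). The number excluded must therefore be printed. Leaving the cell blank avoids the issue.

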13.1.1. Concentration-Time Data

Individual uncorrected and baseline corrected plasma L-dopa concentration-time data will be listed for each subject with actual sampling time (for placebo subjects only uncorrected concentrations will be listed). Plasma uncorrected and baseline corrected concentration-time data will be summarized by treatment and nominal sampling time point with descriptive statistics (number of non-missing observations, arithmetic mean, SD, median, minimum, maximum, geometric mean and coefficient of variation [CV%]). The number of values below limit of quantification (BLQ) will also be presented.

Concentrations that are BLQ will be treated as zero for the computation of descriptive statistics, except geometric mean. For the calculation of the geometric mean, concentrations that are BLQ will be treated as equal to the limit of quantification (LOQ). Missing values will be omitted from the calculation of descriptive statistics.

Individual and mean uncorrected and baseline corrected L-dopa concentration-time profiles for each dose regimen will be presented graphically on both linear and logarithmic concentration scales. Actual sampling times will be used for the graphical presentation of individual concentration-time data, and nominal sampling times will be used for mean concentration-time plots. For plots with a linear concentration scale, BLQ concentrations will be plotted as zero values. For plots with a logarithmic concentration scale, BLQ and zero mean values will not be plotted.

13.1.2. Plasma Pharmacokinetic Parameters

Pharmacokinetic parameters will be computed from the individual uncorrected and baseline corrected plasma L-dopa concentrations using NCA. For the interim analysis, PK parameters will only be estimated from uncorrected concentration data. For the end of study unblinded analysis, the actual PK sampling times

(presented as actual time from dose, with pre-dose time set to zero) will be used for the PK parameter calculations. For the interim analysis, nominal sampling times will be used. Phoenix WinNonlin v8.1 will be used.

For the estimation of PK parameters, reported concentrations for analysis of uncorrected data, and corrected concentrations for analysis of baseline corrected data that have a value of BLQ prior to the first quantifiable value will be set to 0. Concentrations that have a value of BLQ at the end of the sampling period after C_{max} (i.e., no further quantifiable concentrations) will be set to missing and will not be used for the estimation of PK parameter values. If a BLQ value falls between two quantifiable concentrations, the value will be set equal to the LOQ, unless its exclusion can be justified (e.g., implausibility given the profile observed and known PK properties) at the discretion and justification provided by the PK scientist.

The parameters that will be determined and their definitions are provided in the table below.

Table 1: Plasma Pharmacokinetic Parameters

| Abbreviation | Parameter Definition |
|----------------|---|
| C_{max} | Maximum observed drug concentration. |
| T_{max} | Time to maximum observed drug concentration. If the maximum value occurs at more than one time-point, T_{max} is defined as the first time point with this value. |
| $AUC_{0-0.5h}$ | Area under the drug concentration-time curve, calculated using linear-up log-down trapezoidal summation from time zero to 0.5 hours post INP103 administration. |
| AUC_{0-1h} | Area under the drug concentration-time curve, calculated using linear-up log-down trapezoidal summation from time zero to 1 hour post INP103 administration. |
| AUC_{0-2h} | Area under the drug concentration-time curve, calculated using linear-up log-down trapezoidal summation from time zero to 2 hours post INP103 administration. |

AUC_{0-2h} , C_{max} and T_{max} parameters will also be determined for carbidopa (Cohort 4 only), where sufficient plasma concentration data is available.

In addition to non-compartmental pharmacokinetic analysis, exploratory population pharmacokinetic modelling may be undertaken if deemed appropriate. Analysis methods for this will be detailed in a separate population PK modelling analysis plan.

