Evaluation of ON/OFF (Investigator and self-assessment)		X		X					X	X	X	X	X	X				
Rescue OFF Tx allowed													X					
Usual morning anti-PD medication													X					
MDS-UPDRS Full ^h	X	X ^h		X											X			
MDS-UPDRS (III) motor (Cohorts 1 through 3)		X ⁱ						X ^j	X ^j	X ^j	X ^j	X ^j	X ^j					
MDS-UPDRS (III) motor (Cohort 4)		X ⁱ						X ^j		X ^j	X ^j	X ^j						
Prior and Concomitant Medications	X			X		CONTINUOUS												
Subject Questionnaire ^k													X					
Light Breakfast Offered		X		X														

Visit	1	2	3											4	
Day	Up to -21	Up to -20 to -1	-1	0											7
Window	N/A	N/A	N/A				See Footnotes (and Section 7.4.3)							± 10 mins	± 2 days ^a
Time (min)				Pre-dose	0	5	10	15	30	45	60	90	120	240	
Visit	Screening	Dopamine response	Treatment											Follow-up	
PK Blood Collection ¹ (Cohorts 1 through 3)				X					X		X	X	X		
PK Blood Collection ¹ (Cohort 4) Collected 1 minute prior to timepoint				X		X	X	X	X	X	X	X	X		

^a A +4 day window may be permitted in exceptional circumstances.

^b Prior to V2 and/or V3, subjects may attend the unit the previous evening and be domiciled overnight to allow early morning confirmation of their OFF state and facilitate scheduling of pre and post dosing procedures. Subjects not attending the unit the previous evening will arrive on Day 0.

^c Randomization may be performed on the day of dosing (Day 0) or the evening before (Day -1) for subjects being housed overnight prior to dosing.

^d Subjects should be rested in a recumbent position for ≥ 3 minutes prior to recording of ECGs. Subjects should be supine for at least 3 minutes prior to determination of supine vital signs (including blood pressure), after which they should stand and have only standing blood pressure measured immediately. Staff should be on hand to support subjects if required. ECGs and vital signs should be assessed after UPDRS assessment and PK blood draws. Sites may follow their usual sequence of procedures for recording vital signs and ECG where they occur together. The window allotted for vital signs will be +15 minutes at the 30 and 60 minute post-dose timepoints. The vital signs and ECG collection at 120 minutes may occur up to 180 minutes. Due to variability in assessment length, assessments collected out of window, with the exception of PK samples and UPDRS, will not be considered deviations.

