- ^l Baseline PK samples will be taken within 15 minutes prior to dosing. For Cohorts 1-3; the time window for blood sample collection is ± 5 minutes for the samples through 120 minutes. Actual time samples taken will be used for PK analysis. PK blood draws will occur AS SOON AFTER MDS-UPDRS Part III assessments as possible (even if outside of the ± 5 minute window) and time noted. **FOR COHORT 4 ONLY:** PK sample collection will occur 1 minute prior to the timepoint (samples will be collected at 4, 9, 14, 29, 44, 59, 89, and 119 minutes post-dose). For Cohort 4; the window for blood sample collection is up to +1 minute for timepoints 5 minutes up through 30 minutes and ± 2 minutes for timepoints 45 minutes through 120. PK blood draws will occur IMMEDIATELY PRIOR TO MDS-UPDRS Part III assessments as possible (even if outside of the time window) and time noted.
- ^m Only required if no documented history of an MMSE within 36 months prior to Screening.
- ⁿ A light breakfast should be offered to the patient 30 minutes prior to dosing; see [section 4.7](#).

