7.4.3. After Dosing

The subjects will remain in the study clinic post-dose through to the completion of all scheduled post-dose procedures 240 minutes after dosing.

The subject's usual rescue (anti-OFF [e.g. Madopar rapid]) medication will be permitted from 120 minutes post-dose (once all 120 minute assessments have been completed, but can precede ECG, physical examination and subject questionnaire) – if they are still OFF. In addition, subjects should take their regular anti PD medication (e.g. their regular morning Madopar dose) at 120 minutes post dosing whether or not they have returned to ON.

The following in-patient assessments will be performed after dosing:

1. Adverse Events (including overall dyskinesia rating) and concomitant medications will be continually monitored post-dose.
2. Vital signs will be measured at 30, 60 and 120 minutes post-dose. Blood pressure (supine and standing) and heart rate, respiratory rate and oral temperature (supine only) will be measured at all time points. Vital signs will be collected after MDS-UPDRS assessment (where both procedures are scheduled at the same time point) and will not be deemed protocol deviations if they occur outside the time window at each timepoint.
3. PK blood samples will be collected at 4, 9, 14, 29, (all + 1 minute) 44, 59, 89 and 119 (all \pm 2 minutes at each timepoint) minutes post-dose and will precede UPDRS assessments.
4. MDS-UPDRS III only at 15, 30, 45, 60, 90 and 120 minutes post-dose for Cohorts 1, 2 and 3) and 30, 60, 90, 120 minutes for Cohort 4 (\pm 2 minutes at each timepoint)
5. Investigator and subject self-assessment of ON/OFF at 30, 45, 60, 90, 120 and 240 minutes post-dose (\pm 10 minutes at each timepoint)
6. At 120 minutes, the subject's usual morning dose of all Parkinson's medications should be given following completion of assessments 1-5, regardless of ON/OFF state. In addition, if subject is still OFF, their usual OFF medication may be given (prior to completing assessments 7, 8 and 9).
7. Directed physical examination (including nasal inspection) will be performed at 120-180 minutes post-dose

8. 12-Lead ECG will be performed at 120-180 minutes post dose. In cases where vital signs are scheduled at the same time point, ECG will be completed in sequence with vital signs per the usual practice of the study sites.
9. Subject questionnaire will be completed as the last assessment from 120-180 minutes post-dose

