13.1.3. Statistical Methods for Pharmacokinetic Parameters

PK parameters will be summarized by INP103 dose group using descriptive statistics (number of non-missing observations, arithmetic mean, SD, median, minimum, maximum, geometric mean, coefficient of variation as a percent (CV%) and geometric CV%).

Additional analyses will be performed as deemed necessary upon review of the data.

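### Cohort 4 has eight post-dose PK samples and Cohorts 1–3 have four, yet the SAP tabulates Cmax, Tmax and the AUCs side by side with no common-grid version

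*SAP*

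**What the plan says.** Protocol Table 1 has two PK rows. The row for Cohorts 1–3 is marked at pre-dose, 30, 60, 90 and 120 minutes. The Cohort 4 row is marked at pre-dose and eight later times, with the instruction "Collected 1 minute prior to timepoint". Footnote l states, for Cohort 4 only, that "samples will be collected at 4, 9, 14, 29, 44, 59, 89, and 119 minutes post-dose". It adds: "For Cohorts 1-3; the time window for blood sample collection is ± 5 minutes for the samples through 120 minutes".

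Two other protocol sections do not limit the denser schedule to Cohort 4. Section 7.4.3 says "PK blood samples will be collected at 4, 9, 14, 29, (all + 1 minute) 44, 59, 89 and 119" minutes with no cohort named. Section 6.5.1 gives the matching windows (+1 minute up to 30 minutes, then ±2 minutes), also without a cohort limit.

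SAP 13.1.2 uses one set of definitions for all groups: Cmax and Tmax are the observed maximum and its time, and AUC0-0.5h is "Area under the drug concentration-time curve, calculated using linear-up log-down trapezoidal summation from time zero to 0.5 hours post INP103 administration", with AUC0-1h and AUC0-2h built the same way. SAP 13.1.3 adds: "PK parameters will be summarized by INP103 dose group using descriptive statistics". SAP 7.1 pools placebo subjects from all cohorts into one group, and SAP 6.5.5 and 13.1 provide for placebo PK parameters from uncorrected concentrations. No section mentions the unequal sampling or plans parameters on shared times.

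**The concern.** An observed Cmax, an observed Tmax and a trapezoidal AUC all depend on when blood is drawn. Two groups with the same true concentration profile will show different values if one is sampled at 4, 9 and 14 minutes and the other is first sampled at about 30.

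The exposed comparisons are Cohort 4 against Cohorts 1–3, above all Cohort 2, which has the same 70 mg of L-dopa. Protocol 1.3 suggests that patients may benefit more from nasal carbidopa than from an oral DCI, and Protocol 1.2.1 explains that the formulation was chosen for its fast early rise in plasma L-dopa. A reader will look to early exposure in these two cohorts, which is where the schedules differ most. Any pooled placebo column mixes both schedules (six subjects from Cohorts 1–3, two or three from Cohort 4). SAP 13.1.4 does not say whether Cohort 4 enters the dose-proportionality model. PK characterisation is the first secondary objective, and these tables are its main output.

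**Working it through.** The plan gives no figure to reproduce here. The check applies the SAP's rules to one and the same true profile under both schedules.

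**Inputs from the documents.** Cohorts 1–3: 0, 30, 60, 90, 120 minutes. Cohort 4: 0, 4, 9, 14, 29, 44, 59, 89, 119 minutes. Rule: observed maximum; linear-up log-down trapezoid.

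**Assumptions, not in the documents.** One compartment, first-order absorption, C(t) proportional to exp(−ke(t−lag)) − exp(−ka(t−lag)), scaled to a peak of 1, with ke = ln 2/half-life and ka solved from ln(ka/ke)/(ka−ke) = Tmax − lag. Half-life 60–90 minutes, lag 0 or 10 minutes, pre-dose concentration 0, no noise. No human Tmax is given; the monkey medians for carbidopa formulations in Protocol 1.2.1 include 38–68 minutes. Values at 30 and 60 minutes in Cohort 4 are interpolated, and those at 120 minutes extended log-linearly from the last two samples.

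**What follows from the schedule alone.** In Cohorts 1–3 the earliest in-window sample is at 30 − 5 = 25 minutes, so no earlier in-window Tmax can be observed. AUC0-0.5h rests on at most one post-dose sample: with a draw at 30 minutes and C30 ≥ C0 it is 0.25 h × (C0 + C30). If the draw falls after 30 minutes, which footnote l allows, no post-dose sample lies inside the interval.

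**Worked case: half-life 90, Tmax 45, no lag.** Concentrations at 4, 9, 14, 29, 44 minutes are 0.246, 0.483, 0.658, 0.934, 1.000; interpolated C30 is 0.938.
- Cohort 4 AUC0-0.5h (minutes × peak): 0.49 + 1.82 + 2.85 + 11.94 + 0.94 = 18.04.
- Cohorts 1–3: C30 = 0.943, so 15 × 0.943 = 14.15.
- Ratio 18.04/14.15 = 1.28.
- Cmax: 1.000 at 44 minutes against 0.968 at 60 minutes, ratio 1.03.

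**Same case with a 10-minute lag.** Concentrations at 4, 9, 14, 29, 44 minutes are 0, 0, 0.320, 0.889, 1.000; interpolated C30 is 0.896.
- Cohort 4: 0 + 0 + 0.80 + 9.07 + 0.89 = 10.76.
- Cohorts 1–3: 15 × 0.906 = 13.59.
- Ratio 0.79. The direction reverses.

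**Cohort 4 / Cohorts 1–3 ratios at half-lives 60 and 90 minutes:**

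| True Tmax, lag (min) | AUC0-0.5h | Cmax | AUC0-2h | Observed Tmax, Cohorts 1–3 / Cohort 4 |
|---|---|---|---|---|
| 15, 0 | 1.86–1.89 | 1.09–1.12 | 1.16–1.19 | 30 / 14 |
| 30, 0 | 1.44–1.46 | 1.00 | 1.09 | 30 / 29 |
| 45, 0 | 1.25–1.28 | 1.03–1.04 | 1.05 | 60 / 44 |
| 60, 0 | 1.17–1.19 | 1.00 | 1.03 | 60 / 59 |
| 68, 0 | 1.15–1.16 | 1.00 | 1.03 | 60 / 59 |
| 30, 10 | 0.91–0.93 | 1.00 | 0.99 | 30 / 29 |
| 45, 10 | 0.78–0.79 | 1.04–1.06 | 0.98 | 60 / 44 |
| 60, 10 | 0.74–0.75 | 1.00 | 0.98 | 60 / 59 |
| 68, 10 | 0.73 | 1.00 | 0.98 | 60 / 59 |

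A 5-minute lag with Tmax 38–68 minutes gives 0.94–1.11 for AUC0-0.5h. Stepping Tmax minute by minute from 30 to 68 raises the largest noise-free Cmax ratio from 1.06 to 1.08 (10-minute lag). With independent sample noise of CV 20–40% (half-life 90, no lag, Tmax 20–53 minutes) the Cmax ratio is 1.05–1.25, because eight samples give more chances of a high maximum.

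**Check of the remedy.** Restricting Cohort 4 to 29, 59, 89 and 119 minutes, over the same half-lives and lags, brings the ratios to about 0.98–1.01 (Cmax), 1.00–1.04 (AUC0-0.5h) and 1.00–1.01 (AUC0-2h).

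**The case against.** The strongest reply has four parts.

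*The analysis is descriptive.* SAP 3.3 and 3.4 state no PK hypotheses, and no Cohort 2 versus Cohort 4 test is planned. This stands: no test is invalidated. But the groups are still tabulated together, and a descriptive table should not contain a difference created by the sampling times.

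*Matched-time concentrations are already shown.* SAP 13.1.1 summarises concentrations by nominal time, and Cohort 4's draws map to nominal 30, 60, 90 and 120 minutes. This stands for concentrations. It does not help the derived parameters, and using actual times does not supply the missing early samples. Population PK (SAP 13.1.2) is optional only.

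*The large figures need early peaks.* This stands. For Tmax 30–68 minutes the effect on AUC0-2h and noise-free Cmax is small, and those two, with Tmax, are the named secondary endpoints. AUC0-0.5h is the worst affected and is not one of them, although the SAP tabulates it.

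*Protocol 6.5.1 and 7.4.3 could mean that all cohorts have eight samples.* If so, the problem disappears. Footnote l's explicit restriction, and the fact that the windows in those sections match only its Cohort 4 windows, make Table 1 the likelier reading.

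A reader might infer that the artefact necessarily favours Cohort 4. The documents do not support that: the sign for AUC0-0.5h turns on an absorption lag that they do not give. Nor do they support a Tmax floor of 30 minutes in Cohorts 1–3, since the window admits 25. Nor would equal sampling let the Cohort 2 versus Cohort 4 contrast isolate the effect of nasal carbidopa: the cohorts are sequential and not randomised against each other, and they differ in DCI, its route and its timing.

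**Conclusion.** The point holds as a reporting defect worth correcting before the final analysis. On the schedules in Table 1 and footnote l, Cohort 4 and Cohorts 1–3 would show different Cmax, Tmax and AUC values from sampling alone, and the SAP neither adjusts for this nor warns of it.

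The size depends on a profile the documents do not supply. Under the assumptions above, AUC0-0.5h can be off by a factor of about 1.15–1.9 upward or 0.73–0.93 downward, and so cannot be compared across the two schedules. Tmax is not comparable where the peak is early or falls between the sparse times. AUC0-2h (0.98–1.09) and noise-free Cmax (about 1.00–1.06 at the tabulated peaks, at most 1.08) are only modestly affected for Tmax 30–68 minutes; both shift more with an early peak, and Cmax also with noisy samples. Comparisons among the active arms of Cohorts 1–3 share one schedule and are not affected, and the interim analysis covers only Cohorts 1 and 2. Confidence is high that the schedules differ and low on the magnitude.

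**What to change.** In SAP 13.1.2–13.1.3, add a common-grid version of Cmax, Tmax and the AUCs for every table or figure in which Cohort 4, active or placebo, appears beside or is pooled with Cohorts 1–3. Compute it from Cohort 4's pre-dose sample and its samples at nominal 30, 60, 90 and 120 minutes (drawn at 29, 59, 89 and 119), and state how the 120-minute endpoint is reached. Keep the full-sampling Cohort 4 values as a separate presentation, with a footnote that full-sampling AUC0-0.5h and Tmax are not comparable across the two schedules. State in 13.1.4 whether Cohort 4 is included and, if so, on which grid. Reconcile Protocol 6.5.1 and 7.4.3 with Table 1 and footnote l.

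The cost is one further non-compartmental run on existing data and some additional tables. The common-grid version ignores Cohort 4's early samples, which matter for a product meant to act quickly; they remain in the full-sampling table. The change removes only the sampling artefact, not the other differences between Cohorts 2 and 4.
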